## **11.2. Sample Size Determination**

### **11.2.1. Sample Size Assumptions**

The fixed sample size calculation is based on the primary endpoint, percentage of ELLIPTA doses taken (daily adherence) between Months 4 and 6 as determined by the maintenance sensor and has approximately 90% power to detect an absolute difference of 15% in the primary comparison. The treatment difference is based on the limited published data [[Charles](#), 2007, [van Boven](#), 2016]. This assumes a conservative standard deviation of 28% (based on a previous study [[Charles](#), 2007]) and significance declared at the two-sided 5% level.

Approximately 432 patients will be randomised in order to obtain at least 380 subjects (i.e. 76 subjects per arm) with available data over the last three months of the treatment period, in anticipation of a 12% drop-out within the first three months. Subjects will be randomised to one of five treatment arms with a ratio of 1:1:1:1:1.

Using the above assumptions the smallest observed effect predicted to result in a statistically significant difference between treatment groups is 9% (minimum detectable difference).

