**Table 3**

Intercurrent Event Estimation Rules (to be applied sequentially)	Intercurrent Event (IE)	Strategy with Rationale	Estimation Method following IE
1	
None (completed as randomised)
 
Without discontinuation of CIS feedback or ELLIPTA maintenance sensor
 
 
Premature discontinuation from rescue/salbutamol MDI sensor
 
Change of dose of ELLIPTA
 
 
Discontinuation of CIS feedback, but not ELLIPTA maintenance sensor
 
 
Premature discontinuation from App and/or HCP interaction
 
	
Treatment policy:
 
Directly assessed using observed adherence data while ELLIPTA maintenance sensor is in use, regardless of whether the CIS feedback is discontinued.
	Data are available; no imputation required
2	Discontinuation of ELLIPTA maintenance sensor only	
Treatment policy:
 
Without the ELLIPTA maintenance sensor, no CIS feedback is possible, assume
 
 
participants continue to take ELLIPTA as
 
	Jump to Reference (J2R) Imputation

Intercurrent Event Estimation Rules (to be applied sequentially)	Intercurrent Event (IE)	Strategy with Rationale	Estimation Method following IE
		
they would have without the CIS intervention
 
 
adherence will be like that in the control (no CIS feedback) group
 
	
3	Discontinuation of ELLIPTA	Whilst on treatment:	Follow-up after ELLIPTA discontinuation is excluded, i.e. no data; adherence is weighted by proportion of months 4 to 6 for which data is included*
4	Premature withdrawal from the study, not related to ELLIPTA discontinuation or CIS, and concurrent with discontinuation of the ELLIPTA maintenance sensor	Hypothetical:	Missing at Random (MAR) Imputation

* Discontinuation of ELLIPTA prior to the start of month 4 will lead to a participant being excluded from the primary analysis
			

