#### **7.1.4.2. Events following premature discontinuation of the ELLIPTA maintenance sensor**

It is assumed that participants would continue to take ELLIPTA as they would have without the CIS intervention (J2R imputation) following discontinuation of the ELLIPTA maintenance sensor.

It is assumed that ELLIPTA treatment is no longer appropriate if the participant discontinues ELLIPTA but remains in the study or withdraws for a reason related to ELLIPTA. The ELLIPTA adherence endpoint is no longer considered relevant and subsequent follow-up is excluded from the analysis, with participants weighted in the analysis by the proportion of months 4 to 6 for which data is included.

It is assumed that participants would continue to take ELLIPTA as they would have with their allocated CIS intervention (MAR imputation) following concurrent discontinuation of the ELLIPTA maintenance sensor and withdrawal unrelated to ELLIPTA or CIS.

See Section 10.5.3.1 ELLIPTA Device Sensor Assessments for further derivation details.

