- If the sensor is in use for at least a day within a month, m1>0 then let the analysis value be a combined value (weighted average) of the J2RA observed and J2RB imputed values, by taking a proportion of each value based on the proportion of days sensor was still in use and discontinued whilst on ELLIPTA respectively;

Analysis value =  $m1/m1+m2 \times (\text{value from J2RA}) + m2/m1+m2 \times (\text{value from J2RB})$

Note the weight is,  $m1 + m2$

- Else if the sensor was not used in the month, m1=0 then let the analysis value be the imputed value,

Analysis value = value from J2RA dataset (which is the imputed value)

Implement special cases of J2R post-discontinuation of ELLIPTA by identifying participants where ELLIPTA is prematurely discontinued and the participant concurrently withdraws from the study, and ELLIPTA discontinuation reason is not related to ELLIPTA:

Percentage of ELLIPTA doses taken (daily adherence) Endpoint

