
 
If the sensor is in use for at least a day within a month, <math>m1>0</math> then let the analysis value be a combined value (weighted average) of the J2RA observed and J2RB imputed values, by taking a proportion of each value based on the proportion of days the sensor is in use and not in use in that month  <math display="block">\text{Analysis value} = m1/m4 \times (\text{value from J2RA}) + (m2+m3)/m4 \times (\text{value from J2RB})</math> Note the weight is, <math>m4</math>
 
Else if the sensor was not used in the month, <math>m1=0</math> then let the analysis value be the imputed value,  <math display="block">\text{Analysis value} = \text{value from J2RA dataset (which is the imputed value)}</math>
 
 
Implement special case of MAR post-discontinuation of ELLIPTA by identify participants where ELLIPTA is prematurely discontinued and the participant concurrently discontinues the maintenance eSensor and concurrently withdraws from the study, and ELLIPTA discontinuation reason is not related to ELLIPTA and study withdrawal is not related to CIS.
 
Where ELLIPTA has not been discontinued after the sensor but on the same day, <math>m2=0</math>.
 
 
If the sensor is in use for at least a day within a month, <math>m1>0</math> then let the analysis value be a combined value (weighted average) of the J2RA observed and MARB imputed values, by taking a proportion of each value based on the proportion of days the ELLIPTA was in use and not in use in that month  <math display="block">\text{Analysis Value} = m1/m4 \times (\text{value from J2RA}) + m3/m4 \times (\text{value from MARB})</math>
 
Else  <math display="block">\text{Analysis Value} = m1/m4 \times (\text{value from J2RA}) + m3/m4 \times (\text{value from MARA})</math>
 
 
Note the weights are <math>m4</math>

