
STEP 5: Primary and Secondary Percentage of ELLIPTA doses taken Endpoints calculation
 
The calculations presented in the previous steps support the final derivation of the following primary and secondary endpoints, the percentage of ELLIPTA doses taken between
 
 
the beginning of Month 4 and the end of Month 6
 
the beginning of Month 1 and the end of Month 6
 
the beginning of Month 1 and the end of Month 3
 
 
For participants who complete the study treatment (i.e. no premature discontinuation of ELLIPTA Relvar/Breo) during the endpoint period of interest:
 
Analysis Endpoint is the average of monthly Analysis Values over the number of months in the endpoint period of interest, i.e.
 
 
Month 4 to Month 6
 
Month 1 to Month 6
 
Month 1 to Month 3
 
 
For participants who prematurely discontinue ELLIPTA during the endpoint period of interest for reasons related to ELLIPTA, then the weight is the total duration on ELLIPTA within the endpoint period of interest and applied to each analysis month based on the duration within that month. This weight should be applied to each monthly Analysis value within the period of interest and results summed together to produce the final endpoint/response variable for modelling within macro Part 3.

Percentage of ELLIPTA doses taken (daily adherence) Endpoint
---

Note the weight is, total duration of ELLIPTA use within the period of interest . The proportion of weight to apply per monthly Analysis value is  $m1+m2/\text{total duration of ELLIPTA use within the period of interest}$

For participants who prematurely discontinue ELLIPTA during the endpoint period of interest for reasons not related to ELLIPTA or CIS, or just related to CIS, the MAR or J2R imputation assumes participants would have continued taking ELLIPTA until the end of the period of interest. The weight is the total duration within the endpoint period of interest. This weight will be applied to each monthly Analysis value within the period of interest and results summed together to produce the final endpoint/response variable for modelling within macro Part 3.

Note the weight is, total expected ELLIPTA duration within the period of interest. The proportion of weight to apply per monthly Analysis value is  $m1+m2+m3/\text{Total expected ELLIPTA duration within the period of interest}$ .

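### SAP Step 5 omits the concurrent-withdrawal condition, so a participant who stops ELLIPTA for an unrelated reason and stays in the study has two conflicting primary-endpoint values and weights

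*SAP*

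**What the plan says.** Four places in the SAP agree on what follows an ELLIPTA stop.

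- **Table 3, rule 3** covers discontinuation of ELLIPTA without distinguishing reasons: "Follow-up after ELLIPTA discontinuation is excluded, i.e. no data". The weight is the share of Months 4 to 6 that is included. A footnote removes anyone who stopped before Month 4 from the primary analysis.
- **Section 7.1.4.2** assumes that "ELLIPTA treatment is no longer appropriate if the participant discontinues ELLIPTA but remains in the study", and drops the later follow-up.
- **The schematic in 10.5.3.1** shows no data after the stop for pattern D (sensor and ELLIPTA stopped together, no concurrent withdrawal).
- **Step 4** uses J2R after an ELLIPTA stop by "identifying participants where ELLIPTA is prematurely discontinued and the participant concurrently withdraws from the study", and only where the reason is unrelated to ELLIPTA. MAR additionally needs the sensor to stop concurrently and the withdrawal to be unrelated to CIS. These cases carry weight m4, the whole month. The default weight is m1+m2, the days on ELLIPTA.

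Step 5, the final derivation, has two branches for those who stop ELLIPTA in the period. ELLIPTA-related reasons get m1+m2. For stops "for reasons not related to ELLIPTA or CIS, or just related to CIS, the MAR or J2R imputation assumes participants would have continued" to the end of the period, each month gets m1+m2+m3 and the participant gets the full period as weight. Neither branch mentions withdrawal.

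**The concern.** A program that follows Step 5 cannot reach the no-data result for an unrelated stop. Step 4's default fills any month without sensor use with the J2RA value, and only a zero weight in Step 5 would remove it. The unrelated-reason branch gives it full weight instead. Control-arm values then enter the primary endpoint where the while-on-treatment strategy says nothing should.

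The Months 1 to 3 and 1 to 6 endpoints go through the same step, and the binomial GLM sensitivity analysis takes over the same weights, so it would not expose the discrepancy. If the choice is left open, it will be made in programming, possibly after results are visible.

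**Working it through.** **1. The plan's own figures, for scale.** Protocol 11.2.1 gives 76 per arm, a "conservative standard deviation of 28"%, "approximately 90% power to detect an absolute difference of 15% in the primary comparison", and "significance declared at the two-sided 5% level".

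- Standard error of the difference: 28 × √(2/76) = 4.54.
- Power: Φ(15/4.54 − 1.96) = Φ(1.34) = 0.910 (0.907 by noncentral t). The stated figure reproduces.
- Smallest significant difference: 1.96 × 4.54 = 8.9, stated as 9.

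**2. Test case.** Sensor and ELLIPTA stop after day 15 of Month 4 for an unrelated reason, and the participant stays in the study. Own adherence is 80% (assumed). Months are 28 days (SAP Table 5), so the period is 84 days.

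| Month | m1 | m2 | m3 |
|---|---|---|---|
| 4 | 15 | 0 | 13 |
| 5 | 0 | 0 | 28 |
| 6 | 0 | 0 | 28 |

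**3. Table 3 rule 3.** Only 15 days count. Value 80%; weight 15/84 = 0.18.

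**4. Steps 4 and 5 as written.** The Step 4 default for Month 4 is 15/15 × 80 = 80. Months 5 and 6 take the J2RA value R. Step 5 weights each month by 28/84, so the value is (28×80 + 28R + 28R)/84, with weight 84/84 = 1.00.

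| R (assumed) | Step 5 value | Table 3 value |
|---|---|---|
| 50 | 60.0 | 80 |
| 60 | 66.7 | 80 |
| 70 | 73.3 | 80 |

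The weight differs by a factor of 84/15 = 5.6. Month 4 also counts for 28 days although its value rests on 15.

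**5. The SAP's own example values.** The second worked example under Step 4 has Month 4 = 75, Month 5 observed = 83 over 15 days, Month 5 J2RB = 77 and Month 6 J2RA = 77. Apply these to a stop after day 15 of Month 5 without withdrawal:

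- Table 3: (28×75 + 15×83)/43 = 77.8, weight 43/84 = 0.51.
- Step 4 default plus Step 5: (75 + 83 + 77)/3 = 78.3, weight 1.00.
- With the J2R special-case formula for Month 5, (15×83 + 13×77)/28 = 80.2, so (75 + 80.2 + 77)/3 = 77.4, weight 1.00.

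The value hardly moves here, because observed and imputed adherence are close. The weight roughly doubles.

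**6. Effect on an arm mean.** Take one such participant (test case) among 76, as an unadjusted weighted mean, with R = 60.

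- Other 75 average 80 (assumed): 80.00 under Table 3; (75×80 + 66.7)/76 = 79.82 under Step 5. Shift 0.18.
- Other 75 average 75 (assumed): (75×75 + 0.179×80)/75.179 = 75.01 under Table 3; (75×75 + 66.7)/76 = 74.89 under Step 5. Shift 0.12.

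With R from 50 to 70 the shift runs from 0.26 to 0.09 in the first case (80 − 79.74; 80 − 79.91) and from 0.21 to 0.03 in the second (75.01 − 74.80; 75.01 − 74.98).

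**The case against.** **Step 5 may be meant to inherit Step 4's condition.** It says it builds on the preceding steps, and it speaks of imputation that Step 4 defines after an ELLIPTA stop only for concurrent withdrawal. The one CIS-related reason the SAP lists is also a study-withdrawal reason, which suggests the author had withdrawers in mind. This is a fair account of intent. But Step 5 does not say so, and its two branches between them cover every ELLIPTA stop in the period. If that was the intent, the edit only records it.

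**The group is small.** Protocol Section 8 says that those who permanently discontinue ELLIPTA should be withdrawn, and the rationale for Amendment 01 reports a dropout rate well below expectation. This stands as to numbers. It does not empty the class: SAP 10.5.1 says that participants who stop Relvar/Breo may continue in the study, Protocol Appendix 5 keeps liver-stop participants in for follow-up, and pattern D is drawn for them. A reader might infer that the class is common, because withdrawal may be recorded later than the last dose. The documents give no dates or counts that support this.

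**Same-day withdrawal.** A reader might take Step 4's note, "Where ELLIPTA has not been discontinued after the sensor but on the same day", to mean that withdrawal must fall on the day of the ELLIPTA stop, so that any later early-withdrawal visit breaks concurrency. The note compares ELLIPTA with the sensor and serves to set m2 to 0. The adherence text leaves concurrent withdrawal undefined. The clear conflict is therefore the participant who stays in the study.

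**Conclusion.** The conflict is in the current SAP text and holds on any definition of concurrent for a participant who remains in the study. For the primary endpoint it is confined to stops in Months 4 to 6 for a reason not related to ELLIPTA. In the test case the value differs by 6.7 to 20 points (80 − 73.3; 80 − 60.0) and the weight 5.6-fold. With the SAP's example values, the difference is about half a point and a doubled weight.

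At arm level the shift is about 0.1 to 0.2 points per such participant at an imputed value of 60, or 0.03 to 0.26 over 50 to 70. This is small against the 9-point smallest significant difference. These sizes rest on assumed adherence values, and the number of such participants is unknown. A reader might infer that the trial's conclusion is in doubt; nothing here supports that. The point is that a stated rule contradicts the stated strategy and leaves the endpoint without a unique definition, which should be settled before unblinding.

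**What to change.** In Step 5, restrict the m1+m2+m3 full-weight rule to participants who meet Step 4's special-case conditions: an ELLIPTA stop with concurrent study withdrawal and a reason not related to ELLIPTA. Give every other ELLIPTA stop the m1+m2 weight, as in Table 3 rule 3. Report the number per arm in each class.

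State before unblinding how concurrency is determined from the recorded dates. No particular window is proposed; the documents give no basis for one, and the choice is the sponsor's.

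The cost is a short SAP edit and one condition in the program. The downside is that a few participants get a smaller weight. If five per arm (assumed) had weight 0.51, the effective size would be 76 − 5 × (1 − 43/84) = 73.6 per arm, and power would be 90.1% against 91.0%.

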**Part 1B Macro Seed for Parameter Estimation Using Bayesian MCMC Procedure**

Endpoint	Input Dataset	Macro Seed
Percentage of Daily Adherence	Observed Dataset A	2124
	Observed Dataset B	5071

## Part 2B Macro Seeds for Multiple Imputation of Datasets

Endpoint	Multiple Imputation Method	Macro Seed	Output Dataset
Percentage of Daily Adherence	MAR	8517	MAR Dataset A
	J2R	6888	J2R Dataset A
	MAR	6388	MAR Dataset B
	J2R	8674	J2R Dataset B

### 10.5.3.2. MDI Device Sensor Assessments

[figure not shown]
Percentage of Rescue Free Days Endpoint
Overview of Calculation

 
1. Create a dataset (Observed Data A) to calculate the monthly observed percentage of MDI rescue free days values (from month 1 to month 6) accounting for the following,             
 
a. number of days MDI rescue medication was used (at least once per day)
 
b. number of days post MDI rescue use sensor permanent discontinuation
 
c. the intermittent missing daily MDI rescue use data due to device incident
 
d. MDI Rescue free days (i.e. none of the above).
 
 
 
2. Duplicate the observed monthly MDI rescue free values dataset (Observed Dataset A). Using the values in the duplicate dataset (Dataset B), impute the month where the sensor was permanently discontinued before the end of that month (and therefore presents a monthly adherence rate based on partly observed sensor data for that month) as missing unless the participant is a study completer.
 
3. Using each of the two observed datasets (Observed Dataset A and Observed Dataset B), create four separate imputed datasets (J2R-Dataset A, J2R-Dataset B, MAR-Dataset A, MAR-Dataset B) that account for the two imputation methods (J2R or MAR) that may be applied to participants data after discontinuation of the MDI rescue sensor or withdrawal from study. Imputation will be carried out using observed monthly MDI rescue free rates for months 1 to 6. 1000 draws will be used. Completely missing intermediate monthly values will be assumed MAR. The multiple imputation will be implemented using the methods described in Carpenter, 2013, using the macros (Part1A, Part1B, Part2A and Part2B) available from https://missingdata.lshtm.ac.uk/2017/04/06/qsk-five-macros/ using seeds documented in the RAP for the respective endpoint.
 
4. The Observed Datasets (A and B), imputed datasets (J2R-Dataset A, J2R-Dataset B, MAR-Dataset A, MAR-Dataset B) and the timing of the intercurrent events; permanent discontinuation of the MDI rescue sensor and withdrawal from study; will be used to create an analysis dataset (Dataset C) that identifies the proportion of each month to be assigned as observed data, J2R imputed data or MAR imputed data. The strategy for handling intercurrent events is described in Section 7.2.2.3 Strategy for Intercurrent (Post-Randomisation) Events.  Within each imputation draw, for each missing month, the observed and any imputed data will be combined to provide a percentage of rescue free days value. The values for months 4 to 6 will be combined to create the value for the respective secondary endpoint analysis and the weight to be assigned to each participant.
 
5. Analyse using Multiple Imputation macro Part3
 


- a. Perform ANCOVA on the endpoint for each imputed dataset to obtain treatment effect estimate and standard error
- b. Combine estimates across imputations using Rubin's rules

[figure not shown]
### Percentage of Rescue Free Days Endpoint

The intercurrent events identified as part of this secondary endpoint estimand and derivation are detailed in full in Section 7.2.2.3 Strategy for Intercurrent (Post-Randomisation) Events. Below are two schematics of the intercurrent event patterns and their estimation rules.

### Intercurrent Event Patterns

### Intercurrent Event 'Estimation Rules' 1-4

a. J2R imputation if withdrawal related to CIS; MAR imputation if withdrawal not related to CIS

Percentage of Rescue Free Days Endpoint
Intercurrent Events related to CIS
In order to implement the intercurrent event strategy detailed in Section 7.2.2.3 Strategy for Intercurrent (Post-Randomisation) Events, it is necessary to determine if and when the reasons for permanent discontinuations related to CIS occur.
The date and reason for withdrawing from the study will be determined from the study conclusion page of the eCRF.
Study discontinuation reasons classified as related to CIS are as follows:

 
Withdrew consent – dissatisfaction with the connected inhaler system (CIS)
 

Percentage of Rescue Free Days Endpoint
Monthly Percentage of Rescue Free Days - Calculation
STEP 1: Creating the observed adherence dataset (Observed Dataset A)
To determine the monthly observed percentage of rescue free days values (Observed Dataset A) the following should be applied for each month:
For Baseline Analysis Month, for each participant create a count of each of the following types of Days
D1 = Rescue use recorded
D2 = Device incident
D3 = Post discontinuation of MDI rescue sensor
D4 = MDI rescue free
D5=D1 + D2 + D3 + D4, i.e. The total number of days within the Baseline Analysis Month; the total number of days between Beginning Timepoint and Ending Timepoint as defined in Table 5 in Section 10.2 Appendix 2: Assessment Windows .
For Analysis Month 1, 2, 3, 4 and 5, for each participant create a count of each of the following types of days:
D1 = Rescue use recorded
D2 = Device incident
D3 = Post discontinuation of MDI rescue sensor
D4 = MDI rescue free
D5 = D1 + D2 + D3 + D4, i.e. The total number of days within the Analysis Month; the total number of days between Beginning Timepoint and Ending Timepoint as defined in Table 5 in Section 10.2 Appendix 2: Assessment Windows .
For Analysis Month 6, for each participant create a count of each of the following types of days:
D1 = Rescue use recorded
D2 = Device incident
D3 = Post discontinuation of MDI rescue sensor
D4 = MDI rescue free
D5 = D1 + D2 + D3 + D4, i.e. the total number of days within Analysis Month 6; the total number of days between Beginning Timepoint and Ending Timepoint as defined in Table 5 in Section 10.2 Appendix 2: Assessment Windows .

### Percentage of Rescue Free Days Endpoint

The following observations from the sensor and eCRF will be required to determine the above Days and the differences between missing at random due to device/sensor incident and non-adherent days.

- Device malfunction date
- Sensor malfunction date
- Permanent discontinuation of MDI rescue sensor
- First and last individual sensor synchronisation dates

The first and last individual sensor synchronisation dates will be provided in the sensor dataset. These dates will be used to assess whether missing observations are due to rescue free days or data being missing at random due to device/sensor malfunction.

For each Analysis Month, the Observed MDI rescue free days (%) for that month will be calculated as follows:

$$\text{Monthly observed MDI rescue free days (\%)} = \left( \frac{D4}{D5 - D2 - D3} \right) \times 100$$

